5.3 Frailty Measures

We will use a combination of validated frailty assessment tools which are listed in Appendix A and summarized below in Tables 1 and 2. Using both the phenotype and cumulative deficit models (see above) is beneficial to provide more validity for a frailty assessment, and cross validity between the two models has been established.^{11,17} At current, there is still some debate as to the true clinical definition of frailty, and different studies have used different approaches to assess the frailty.¹¹ Using both models will allow for a more rigorous evaluation.

Table 1: Summary of cumulative deficit domains

Domain	In-person and Virtual Administration	Variable type	Cut-point
Functional Status in ADLs^{12,18}	Patient questionnaire #1-14 ^{12,19,20}	Binary	See Appendix A
Overall self assessment of health and performance Status^{12,21}	Patient Questionnaire #15-20, verified by physician report	Continuous	See Appendix A
*Weight loss^{3,11,12}	Patient questionnaire #21	Binary	See Appendix A
*Self-reported exhaustion^{3,11,12}	Patient questionnaire #24-25	Continuous	See Appendix A
Psychological Status^{12,18}	Patient questionnaire #26-28	Continuous	See Appendix A

Comorbidity ^{12,18-20}	Medical Record Review	Continuous	See Appendix A
*Physical Function and BMI ^{3,11,12}	Grip strength, gait speed, and BMI recorded by research assistant	continuous	See Appendix A
Cognition ¹⁸	Clock in the Box ²² (in-person) or Clock Draw (virtual) and MoCA ¹⁴ delayed recall administered by research assistant	continuous ¹²	See Appendix A

*Also included in phenotype assessment

Table 2: Summary of phenotype questions

Domain:	Measure:	In-person and Virtual Administration:	Results:
Weight Loss	In last year, weight has decreased by greater than or equal to 10 lbs or 5% of body weight ^{3,11}	Patient questionnaire #21 and medical record review by research assistant	Positive: Patient has lost 10 lbs or more in last year ^{3,11} Negative: Patient has not lost 10 lbs or more in last year ^{3,11}
Self-reported Exhaustion	Two questions from the CES-D Scale ²³ about exhaustion	Patient questionnaire #24-25	Positive: Patient answers: “most of the time” for either question Negative: Patient answers: “some of the time” or “rarely” for both questions ³

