Energy Expenditure	Ability to walk ¹¹	Patient questionnaire #4 and ability to complete gait speed test at time of assessment	Positive: Needing assistance with walking or being unable to walk Negative: No assistance needed for walking ¹¹
Gait speed	NIH 4 meter gait speed test ^{24,25}	Administered by research assistant or trained caregiver	Positive: Rapid gait speed less than or equal to cut-points provided by Gill et al. ²⁶ Negative: Rapid gait speed greater than cut-points provided by Gill et al. ²⁶

Grip strength	Jamar Hand Dynamometer (Sammons Preston Roylan, Bolingbrook, IL) grip strength test ²⁶	Administered by research assistant or estimated by the following question: Do you have difficulty gripping with your hands (e.g. opening a jar)? Yes or No.	Positive: Average strength less than or equal to the cut-points provided by Fried et al., ³ or self-reported difficulty gripping Negative: Average strength greater than the cut-points provided by Fried et al., ³ or no self-reported difficulty gripping
----------------------	---	---	--

We will calculate two scores for frailty; one based on the cumulative deficit model and the other on the phenotype model. If patient's score as frail or pre-frail by either method they will be eligible for evaluation by a geriatrician.

For the Cumulative deficit score (table 1), the cumulative total of deficits is determined by adding all of the deficits that are present (deficit present = 1, deficit absent = 0, and for some variables, partial deficit = 0.25, 0.5, or 0.75) and dividing the result by the total number of items in the index. This study will use a frailty index comprising of 43 items (see appendix A). Of note, up to 92 symptoms can be assessed, although as few as 30 items can be used without loss of predictive validity.^{18,20} Furthermore, the actual composition of the index is not crucial. As long as a sufficient number of variables are used, the variables can be selected at random and still yield comparable results.²⁷ After calculating a total frailty score on the 0-1 scale, cut-points of 0-0.2 for "robust", 0.2-0.35 for "pre-frail", and 0.35-1.0 for "frail" will be used to categorize patients, as was done in the Sheppard study.¹⁶

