6.0 ANALYTIC CONSIDERATIONS

6.1 Specific Aim 1

We will first perform descriptive analyses of covariates of frailty/pre-frailty in our population, including age, gender, race-ethnicity, and disease type. Means and proportions will be used to describe patient characteristics, individual and summary frailty responses, baseline clinical data, and treatment assignment. We will identify variables that are associated with the outcomes of interest using Kaplan-Meier curves and log-rank tests. Given limited numbers of patients and other study resources, we will plan to combine the frail and pre-frail groups in our analyses for Aim 1 (frail/pre-frail versus robust), but if power allows, we will also compare outcomes for all three groups (frail versus pre-frail versus robust). We will use the tests above for univariate analyses to determine whether any of the relevant geriatric domains, socio-demographic factors, or clinical data are associated with choice of treatment, length of time in the hospital and survival. We will also perform univariable and multivariable analyses to determine if frailty interacts with other patient characteristics to influence outcomes. We will also conduct analyses specific to disease clinics at DFCI (MDS/leukemia versus lymphoma versus myeloma). We will consider a p value < 0.05 to be significant, and all analyses will be carried out using SAS v.9.

6.2 Specific Aim 2

For frail patients, pre-frail patients and the combined cohort, we will create multivariable models to assess the impact of geriatric co-management on the outcomes listed in Table 3, controlling for age, gender, race-ethnicity, and disease type. We will consider a p value < 0.05 to be significant, and all analyses will be carried out using SAS v.9. Of note, we again plan to combine the frail and pre-frail groups in our analysis given limited resources and lack of current data as to whether or not geriatric intervention is more helpful in one of these groups; if power allows (see below), we will also adjust for frail versus pre-frail status.

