8.0 PROJECT TIMELINE

January 2015	Obtain OHRS approval
February 2015	Begin baseline geriatric assessments and randomization
August 2015	Interim analysis for Specific Aim 1
May 2018	Finish enrollment for Specific Aim 2
June 2018 to August 2019	Continuing enrolling participants to Specific Aim 1; Interim analyses for Specific Aim 1; Analysis and abstract write-up for Specific Aim 2
September 2019 to January 2020	Final manuscript for Specific Aim 2
February 2020 to January 2024	Continuing enrolling participants to Specific Aim 1; Interim analyses for Specific Aim 1; Continue follow-up for outcomes.
January 2024 to January 2025	Specific Aim 1 analysis; Final manuscript for Specific Aim 1

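### Section 6.1 calls any p < 0.05 significant across an unlisted Aim 1 screen, with no ranking of tests, no error control and no rule for the interim analyses

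*Combined protocol and SAP*

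**What the plan says.** Section 6.1 plans univariate tests of "whether any of the relevant geriatric domains, socio-demographic factors, or clinical data are associated with choice of treatment", and of the same variables with time in hospital and survival. No list of domains, factors or clinical variables follows. The section adds univariable and multivariable analyses of whether frailty interacts with other characteristics, a three-group frailty comparison if power allows, and this: "We will also conduct analyses specific to disease clinics at DFCI (MDS/leukemia versus lymphoma versus myeloma". One decision rule covers the section: "We will consider a p value < 0.05 to be significant".

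Section 6.3 raises the Aim 1 target from 540 to 1,620 potential patients so that analyses can be stratified by clinic. Section 8.0 lists an Aim 1 interim analysis in August 2015, then "Interim analyses for Specific Aim 1" in June 2018 to August 2019 and again in February 2020 to January 2024, before the final Aim 1 analysis in January 2024 to January 2025. It does not say what the interims test or at what level.

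Section 3.1 gives one Aim 1 hypothesis: frailty predicts survival in low-risk disease, while disease risk dominates in high-risk disease. Section 6.1 does not separate that hypothesis from the screen.

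**The concern.** When many associations are tested at 0.05 each and every p-value below that line counts as a finding, some findings are expected from chance alone. Nothing in the plan tells a reader which Aim 1 result was the pre-stated one and which came from the screen. Clinic-specific and interaction results are the most exposed, because they add many tests in smaller groups. Repeated analysis of accumulating data adds to this if significance is claimed at each look.

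At stake is how the Aim 1 results can be read. Section 2.3 expects the study database to support models of prognosis and toxicity and, in time, individualised therapy, so a list of apparent predictors that cannot be told from noise would have little value.

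**Working it through.** **The plan's own figure.** There is none for Aim 1: no power, no family-wise error rate, no number of tests. The only power figure (section 6.3: 80% for 107 versus 53 patients, 68% versus 85% one-year survival, one-sided 0.05) belongs to Aim 2. It is approximately reproduced with an unpooled-variance test (81.8%) or the arcsine method (78.2%), and has no bearing on this point.

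**Inputs.**
- Per-test level: 0.05 (section 6.1; sidedness not stated).
- Domains: 8, counted from "Table 1: Summary of cumulative deficit domains" in section 5.3.
- Patient factors: 4, from the descriptive sentence of section 6.1 ("including age, gender, race-ethnicity, and disease type"). Using them as screening variables is an assumption.
- Outcomes: 3 (treatment choice, time in hospital, survival).
- Populations: the full cohort, and possibly three clinics. Disease type is assumed not to be tested within a clinic, which removes 1 × 3 outcomes × 3 clinics = 9 tests.

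**Expected false positives at one analysis, nothing associated.** Expected number = tests × 0.05.

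| Predictors assumed | Full cohort only | Full cohort plus three clinics |
|---|---|---|
| 8 domains | 8 × 3 = 24 tests; 1.2 | 24 × 4 = 96 tests; 4.8 |
| 8 domains + 4 factors | 12 × 3 = 36 tests; 1.8 | 12 × 3 × 4 − 9 = 135 tests; 6.75 |

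Interaction tests and other clinical variables are not counted. Each finding is one predictor with one outcome in one population, so the same predictor can be counted more than once.

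**Chance of at least one.** With independent tests, 1 − 0.95^36 = 84% in the full cohort and 1 − 0.95^135 = 99.9% with clinics. Correlation leaves the expected number unchanged but lowers this chance. In a simulation with correlation 0.5 between predictors and between outcomes it was 64% and 96%.

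**If some associations are real.** With half of them real, the expected false positives are 36 × 0.5 × 0.05 = 0.9 in the full cohort and 135 × 0.5 × 0.05 = 3.4 with clinics. With three quarters real, they are 36 × 0.25 × 0.05 = 0.45 and 135 × 0.25 × 0.05 = 1.7.

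**Repeated looks.** Counting one look per listed interim period plus the final analysis gives at least four. By simulation, one null test judged two-sided at 0.05 at every equally spaced look is significant at least once in 12.6% of studies with four looks and 14.2% with five. Three looks give 10.7%. Four looks with an early first one (5%, 35%, 70% and 100% of the information) give 14.6%.

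**The case against.** The strongest reply is that Aim 1 is an observational cohort, that section 7.3 describes the data as a pilot for later projects, and that formal error control in hypothesis-generating work is partly a matter of preference. Some structure also exists: section 3.1 states a hypothesis, section 6.1 names the main contrast (frail/pre-frail versus robust), and Table 3 marks survival as primary. Section 2 reports that frailty markers predict mortality, so a state in which nothing is associated is unlikely.

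Much of this stands, and it limits what can be claimed. A reader might infer that every domain is screened in every clinic and again at every interim, all at p < 0.05. On that reading, four looks give 36 × 0.126 = 4.5 tests ever significant in the full cohort, or 135 × 0.126 = 17 with clinics. The documents do not support this as fact. Section 6.1 refers to relevant domains without listing them and promises clinic-specific analyses without saying that the whole screen is rerun. Section 8.0 gives the interims no content, threshold or decision. Nor does the index size ("This study will use a frailty index comprising of 43 items") justify counting items, since section 6.1 speaks of domains. Section 2.3 links the database to future models, but does not say that variables with p < 0.05 will enter them.

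The reply does not remove the point. The plan never calls the screen exploratory and states a significance rule for it. The primary marker in Table 3 does not settle the ranking for Aim 1: the text of section 5.4 calls all Table 3 outcomes secondary, and section 6.3 ties the primary endpoint to Aim 2.

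**Conclusion.** The concern holds in a limited form. Section 6.1 applies one unadjusted threshold to an open-ended set of tests, does not rank them, and leaves the interim analyses without a rule.

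In the full cohort, the only population in which the screen is explicit, the expected excess is small: 1 to 2 chance findings at domain level. It becomes several only if the screen is also run by clinic. That is a natural reading, given why the sample was enlarged, but it is not stated. Even then the number falls as more of the associations are real. The repeated-look figures apply only if significance is judged at 0.05 at each look.

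A reader might conclude that most Aim 1 predictors will be false, or that the trial's primary result is compromised. Neither follows. The counts are expectations under stated assumptions, and the randomised comparison in Aim 2 is outside this screen. This is a worthwhile, inexpensive improvement to the plan.

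**What to change.** In section 6.1:

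1. Set the section 3.1 hypothesis apart as the primary Aim 1 analysis, tested once, at the final analysis: frail/pre-frail versus robust and overall survival, with the frailty-by-disease-risk interaction that the hypothesis implies. State how the two share the 0.05 level. Making only the full-cohort frailty effect primary would demote the one hypothesis that the plan states.
2. List the predictors to be screened.
3. Label the univariate, clinic-specific and other interaction tests exploratory. Beside each raw p-value, report a Benjamini-Hochberg value for 5% false discovery within a defined family, for example per outcome across predictors and populations. With 12 predictors that is 12 + 11 × 3 = 45 tests per outcome.
4. Report any remaining interim analyses as estimates with confidence intervals and no significance claims. The 2015 and 2018 to 2019 interim periods precede the September 2020 changes that the document describes, so this can cover only what is left and the final analysis. It should be written in before the final analysis is run.

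Every planned analysis stays and no new data are needed. The cost is SAP wording, an extra column in the output, a definition of low and high disease risk (Table 3 lists baseline disease severity without categories), and fewer nominally significant secondary results.

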1.0 SUMMARY

We are interested in measuring the frailty of older blood cancer patients with precision, determining how much it contributes to prognosis compared with clinical disease-specific measures, and determining if co-management by a geriatrician embedded in the oncology clinic can improve outcomes. We thus propose to characterize the prognostic value of frailty as compared to clinical prognostic models for older patients with blood cancers, and, using a randomized design, determine if co-management of frail older adults with blood cancers by an embedded geriatrician reduces frailty and/or improves outcomes such as survival and non-scheduled hospital admissions.

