5.4 Data Collection Procedures

Patients will be approached or contacted by the research assistant either at their scheduled appointment with the DFCI oncologist (in-person) or shortly after that appointment (virtual). The research assistant will then consent the patients and document consent with either the patient's wet-ink signature (in-person) or the signature of the research assistant verifying that verbal consent was given (virtual). The assessment will be conducted in-person or remotely, by phone or video conference, to preserve the safety of our patient population during the ongoing COVID-19 pandemic.

In-person assessments will begin with a 28-item self-report questionnaire (see appendix B) filled out by the patient. Next, the research assistant will administer the delayed recall section of the Montreal Cognitive Assessment (MoCA), clock-in-the-box test, grip strength test, and gait speed test. That will end the in-person frailty assessment. Virtual assessments contain minor changes to accommodate remote completion. The 28-item questionnaire, MoCA recall, and modified Clock Draw are conducted by the research assistant during a telehealth appointment. A patient caregiver will be trained to administer a remote gait speed test with a 4-meter strip of

ribbon that will be mailed in advance. Grip strength will be estimated using the following question: *“Do you have difficulty gripping with your hands (e.g. opening a jar)? Yes or No.”*

At baseline, the research assistant will perform a medical record review to obtain comorbidity information and body mass index. A follow up medical record review will be completed at one year from enrollment in order to obtain the outcome data listed in Table 3, which are all secondary outcomes of interest. There will also be general periodic assessments for overall survival.

Table 3: Summary of outcomes

Outcome:	Timeline for assessment:	Operationalization	Obtained from:
Survival*	6 months, 1 year	Overall survival	Patient medical record and outside records
Disease severity	Baseline	Disease Severity	Patient medical record and outside records
Treatment assignment	6 months	Supportive care only vs. chemotherapy vs. low dose chemotherapy vs. investigational treatment; any disease-modifying treatment versus not	Patient medical record and outside records
Hospitalizations	6 months	Number and length of hospitalizations since enrollment	Patient medical record and outside records

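### Aim 2 tests about seven secondary outcomes in three overlapping cohorts at an unadjusted p < 0.05, so an ineffective intervention has roughly a 24% to 31% chance of showing at least one significant improvement

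*Combined protocol and SAP*

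**What the plan says.** Section 6.2 sets out the randomized comparison in three groups: "For frail patients, pre-frail patients and the combined cohort, we will create multivariable models". These models assess the intervention, and one criterion covers all of them: "on the outcomes listed in Table 3, controlling for age, gender, race-ethnicity, and disease type. We will consider a p value < 0.05 to be" (results below this level are called significant). The section then adds that "we again plan to combine the frail and pre-frail groups in our analysis given limited resources", with adjustment for frail versus pre-frail status only if power allows. It does not say whether the tests are one-sided or two-sided.

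Sections 3.2 and 6.3 name overall survival at one year as the primary outcome, and Table 3 marks survival with an asterisk. Section 5.4 describes the Table 3 outcomes with the words "which are all secondary outcomes of interest". Section 6.3 sets a one-sided 0.05 level, for the primary endpoint only.

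The Summary (1.0) states the purpose broadly, in a sentence that ends with hospital admissions: "determine if co-management of frail older adults with blood cancers by an embedded geriatrician reduces frailty and/or improves outcomes such as survival and non-scheduled hospital".

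**The concern.** The primary outcome and every secondary outcome share one threshold, and the secondaries are examined in three cohorts, one of which is the union of the other two. Nothing in the plan limits how many of these tests may be called significant, makes them conditional on the survival result, or marks them as exploratory.

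The stake is the reading of a trial that is negative on survival. Aim 2 asks whether co-management improves outcomes. Under the text as it stands, one secondary result below 0.05 in any of the three cohorts could be reported as a significant benefit, although the chance of such a result under no effect is several times the level attached to a single test.

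**Working it through.** The plan gives no error rate for this family of tests, so there is no figure of its own to reproduce.

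**Step 1. Count the tests.** Table 3 has 10 rows. Leaving out survival gives 9. Two of those cannot be between-arm outcome tests: disease severity is recorded at baseline, and the content analysis of notes covers only patients randomized to the geriatrician. Seven rows remain. Counted by the measures in the operationalization column:

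- treatment assignment: 2
- hospitalizations: 2 (number, length)
- emergency department visits: 1
- code status: 1
- continuation of care: 3 (visits, length of follow-up, receipt of treatment)
- change in number of medications: 1
- change in blood pressure: 1

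Total: 2 + 2 + 1 + 1 + 3 + 1 + 1 = 11.

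Over three cohorts this is 7 × 3 = 21 or 11 × 3 = 33 tests. Expected false positives at 0.05 are 21 × 0.05 = 1.05 and 33 × 0.05 = 1.65, half of them in the favourable direction if the tests are two-sided.

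**Step 2. Closed-form anchor.** In the combined cohort alone, with independent outcomes:

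- either direction: 1 − 0.95^7 = 0.302; 1 − 0.95^11 = 0.431
- favourable direction, two-sided tests: 1 − 0.975^7 = 0.162; 1 − 0.975^11 = 0.243

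**Step 3. Allow for correlation and overlapping cohorts.** Null z statistics were simulated with a common correlation ρ between outcomes, independently in frail and pre-frail patients. The combined statistic is

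z_combined = √f · z_frail + √(1 − f) · z_pre-frail,

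where f is the frail share. The documents give neither ρ nor f, so both are assumptions: ρ = 0.5 with range 0.7 to 0, and f = 40%. Moving f between 30% and 50% changes the results by less than one percentage point. Two-sided tests use |z| > 1.96. An improvement means z > 1.96, or z > 1.645 if each test is one-sided at 0.05.

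Chance of at least one significant result under no effect:

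| Cohorts | Outcomes | What counts | ρ = 0 | ρ = 0.3 | ρ = 0.5 | ρ = 0.7 |
|---|---|---|---|---|---|---|
| Three | 7 | either direction | 57% | 52–53% | 45% | 36% |
| Three | 11 | either direction | 74% | 67% | 57% | 44% |
| Three | 7 | improvement, two-sided | 34% | 28–29% | 24% | 19% |
| Three | 11 | improvement, two-sided | 48% | 38% | 31% | 23% |
| Three | 7 | improvement, one-sided 0.05 | 56% | 46% | 39% | 31% |
| Three | 11 | improvement, one-sided 0.05 | 72% | 57% | 48% | 37% |
| Combined only | 7 | either direction | 30% | 27% | 23% | 18% |
| Combined only | 11 | either direction | 43% | 37% | 30% | 22% |
| Combined only | 7 | improvement, two-sided | 16% | 14% | 12% | 9% |
| Combined only | 11 | improvement, two-sided | 24% | 19% | 15% | 11% |

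The combined-only results at ρ = 0 agree with the closed forms in Step 2.

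**Step 4. Compare with a single test.** One two-sided test at 0.05 has a 2.5% chance of a false improvement. At ρ = 0.5 the three-cohort figures are about 24/2.5 = 9.6 and 31/2.5 = 12.4 times that. The combined-only figures are about 12/2.5 = 4.8 and 15/2.5 = 6 times.

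**The case against.** The strongest reply is that the plan does have a hierarchy. One-year survival is the named primary outcome, the only powered endpoint and the only outcome in the Aim 2 hypothesis, and the rest are called secondary. Many trials leave labelled secondaries unadjusted, and section 7.3 describes the data as a pilot for larger projects. This stands in part: a reader who inferred that the plan has no hierarchy at all would be wrong. What is missing is narrower, namely error control or ordering among the secondaries. The secondary label gives little protection when 6.2 applies the same rule to every outcome.

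Other stronger readings also fail:

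- A reader might take 45% to 57% as the chance of a spurious improvement. Those figures count differences in either direction, harm included. The improvement figures with two-sided tests are 24% and 31%.
- A reader might count every non-survival row. Two of the nine cannot be compared between arms.
- A reader might treat the and/or in the Summary as a decision rule. It joins reduced frailty to improved outcomes in a general statement of purpose. No section says that one significant secondary establishes efficacy.

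The sentence in 6.2 about combining frail and pre-frail patients could make the combined cohort the main analysis. It does not withdraw the three-cohort models, so the text is ambiguous, and both sets of figures are given above.

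Several rows, such as treatment assignment, code status, continuation of care and blood pressure, have no stated favourable direction, so the improvement figures are approximate. This works both ways: where no direction is fixed in advance, a difference either way could be presented as benefit. Counting only four outcomes and only favourable two-sided results still gives 14% to 21% over three cohorts.

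**Conclusion.** The concern holds in a limited form. About 7 secondary outcomes, or 11 measures, are tested between arms in three overlapping cohorts at an unadjusted p < 0.05, without ordering or an exploratory label. Under no effect, with two-sided tests, the chance of at least one apparent improvement is about 24% (19% to 34%) for 7 outcomes and 31% (23% to 48%) for 11. If the one-sided 0.05 of section 6.3 also governs 6.2, the central values are about 39% and 48%. If only the combined cohort counts, the two-sided values are about 12% and 15%.

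These sizes rest on an assumed 40% frail and an assumed common correlation of 0.5 (range 0.7 to 0). The frail share hardly matters; the correlation matters a good deal. In every version the rate is well above the 2.5% of a single two-sided test. The primary survival comparison is not affected.

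**What to change.** In section 6.2, state that Aim 2 efficacy is concluded only from the primary one-year survival comparison in the combined cohort. Report all other Table 3 between-arm comparisons, and all separate frail and pre-frail results, as exploratory, with effect estimates and 95% confidence intervals and without calling any of them significant.

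A confirmatory secondary should not be added at this stage. The obvious candidate, the non-scheduled admissions named in the Summary, is not defined in Table 3, which records only number and length of hospitalizations. Section 5.1 also says Aim 2 is closed to enrollment, and section 8.0 scheduled its final manuscript for September 2019 to January 2020, so a testing order introduced now would not be prospective. For the same reason, the change governs how results are labelled and interpreted.

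The cost is a few sentences, with no extra patients or data. The downside is that an isolated secondary result below 0.05 can be reported only as exploratory.
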